| Methodology | Randomized, double-blind, placebo-controlled trial |
| Study Duration | 5 years |
| Study Center(s) | Single-center – University of Pennsylvania Treatment Research Center |
| Objectives | To determine the efficacy of varenicline (Chantix™) for the treatment of cocaine dependence |
| Number of Subjects | 200 |
| Diagnosis and Main Inclusion Criteria | Cocaine dependence. Men and women ages 18-65. Subjects must have current DSM IV diagnosis of cocaine dependence and a recent history of cocaine use. Subjects must be in good health and psychiatrically stable. They must have no other current substance dependence except nicotine or alcohol. |
| Study Product, Dose, Route, Regimen | Varenicline (Chantix™), oral 1.0 mg BID. |
| Duration of administration | 12 weeks |
| Reference therapy | Placebo |
| Statistical Methodology | 
Hypothesis 1: Cocaine use will be measured with three-times-weekly urine benzoylecgonine (BE) levels and self-reports of use from the Time Line Follow Back, combined to yield daily use/no-use indicators for each study day. We plan to use a mixed effects model. Mixed-effects models have two parts: a fixed effects component (comprising the explanatory variables included in the model) that describes the mean values of the outcomes across the time points, and a random-effects component defining the variances and covariances of the outcomes. In our models, the primary fixed effects are group, and time, together with possible interaction terms. The effect of time will be broken into linear, quadratic and, possibly, cubic, trends across the 13 weeks. A generalized estimating equations (GEE) model will be used to model the effects of medication group and time on the log-odds of use across the treatment period. The explanatory variables in these models will be a binary factor for medication, and terms for time effects, and group by time interaction
 |

Introduction

This document is a protocol for a human research study. This study is to be conducted according to US and international standards of Good Clinical Practice (FDA Title 21 part 312 and International Conference on Harmonization guidelines), applicable government regulations and Institutional research policies and procedures.

1.1 *Background*

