Before study-specific eligibility criteria are assessed, subjects are asked for their consent. At the consent session, all assessments, lab procedures and information on study medications are fully explained. Subjects are given information about confidentiality, study payments and under what circumstances they may be prematurely discontinued from treatment. Subjects are told that a blood alcohol concentration (BAC) reading will be required at each TRC visit, and that the reading must be below 0.02, otherwise the visit will be rescheduled. If their BAC reading is 0.08 or higher, they will be detained until arrangements are made for them to be escorted home or the reading decreases to an acceptable level (e.g., 0.02). At the end of the session, subjects take a consent “quiz” that can be re-taken until all of the questions are answered correctly. Subjects then give written consent and are given phone numbers of key project staff and a 24-hour emergency number. After signing informed consent, subjects continue with screening assessments to determine if they meet eligibility criteria.

Subsequent screening procedures include blood chemistry, CBC, urinalysis, psychiatric interview, assessment of baseline drug and alcohol use using the Timeline Follow Back, Addiction Severity Index.

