5.3 Method for Assigning Subjects to Treatment Groups

Urn Randomization: We will use urn randomization to stratify subjects across the two experimental conditions. In the randomization scheme, we will stratify subjects on 2 baseline variables: 1. Gender; 2. Cigarette smoking status. We have no reason to suspect gender differences to mediate outcomes; however, it certainly is possible, given our sparse knowledge about female alcohol and drug abusers. Also, because we estimate that fewer than 30% of our final sample will be females, based on TRC census data over the past 5 years, it is imperative that we use gender as one of the urn variables in randomizing.

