16. **Timeline Follow Back Interview** (TLFB) (Sobell and Sobell, 1995). The TLFB is a 15-30 minute, semi-structured interview adapted by our laboratory to collect information about daily cocaine, alcohol, and nicotine use. Critical life events are reviewed retrospectively to prompt recall of cocaine use measured in days used and dollars worth of cocaine used. Nicotine use is measured by number of cigarettes (or other forms of tobacco) per day. Cocaine, and nicotine use are recorded on a personalized calendar. Other drugs and any days spent in a controlled environment are also recorded on the calendar. The TLFB will be given by trained research staff at baseline to cover 3 months immediately preceding treatment entry and will be updated at each research visit to determine any time spent in a controlled environment and cocaine, nicotine, and other drug use during the period since the last visit. The composite of these assessments will be additive over the course of the study so that we will have continuous data on cocaine and nicotine use (Visit 1 through 40).
17. **Treatment Group Prediction Form** Integrity of the study blind will be evaluated by having the nurse or physician, therapist, research staff and subject predict which medication group assignment (active or placebo). (Week 7 and Visit 40).
18. **Treatment Services Review** (TSR) (McLellan et al., 1992). The TSR is a 5-minute interview given by the research staff to record the subject's use of services received in 7 areas covered in the ASI since the last visit. Test-retest reliabilities are high (McLellan et al., 1992a). The measure is given during baseline week, weekly throughout the medication phase, at the end of randomized medication phase and at the end of treatment visit so that there is a continuous record of non-study treatment services throughout the trial (Visits 1,4,7,10,13,16,19,22,25,28, 31, 34, 37, 40). These data will be used to compare utilization of ancillary treatments during the trial in the varenicline and placebo groups.

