6.1 Visit 1 (screening)

All screening procedures are to be completed prior to randomization (visits 1, 2, or 3). They may not necessarily be completed at the exact visit noted below.

Nurse or physician:

1. Informed consent and consent quiz
2. Medical history
3. Physical Exam (PE)
4. Vital signs weight (VITALS)
5. Electrocardiogram (EKG)
6. Concomitant medications (CONMEDS)
7. Adverse Events (AE)
8. CBC and blood chemistry including liver function tests (LFT) and CO2.
9. Urinalysis (UA)
10. Clinical Global Impression Scale, Observer (CGIO)
11. Supplemental questions
12. Clinical Institutes Withdrawal Scale for Alcohol Revised (CIWA AR)

Research staff

1. Breathalyzer (BAL)
2. CO
3. Cocaine Selective Severity Assessment (CSSA)
4. Treatment Services Review (TSR)
5. Minnesota Cocaine Craving Scale (MCCS)
6. Cocaine Craving Questionnaire (CCQ)
7. Fagerstrom Nicotine Tolerance Questionnaire (FNTQ)
8. Brief Substance Craving Scale (BSCS)
9. Multiple Choice Procedure (MCP)
10. Delay Discounting Questionnaire (DD)
11. Risk Assessment Battery (RAB)
12. Symptom Checklist-90-Revised (SCL-90-R)
13. Timeline Follow Back (TLFB)
14. Urine drug screen other than cocaine (UDS)
15. Urinary BE level (qualitative)
16. Cotinine
17. Clinical Global Impression Scale, Subject (CGIS)
18. Urine pregnancy test (UPT)(females)
19. Short Form Health Survey (SF-36)

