7.2 Statistical Methods

Data Analyses: The data analyses will be performed by [name], the CSA Statistician, and his staff. Prior to performing analyses, standard data screening/cleaning procedures will be applied (Tabachnik and Fidell, 2000). These procedures will (1) screen the data for data-entry errors, (2) check for outliers, (3) assess the extent and pattern of missing data, and (4) check that appropriate assumptions of Normality are met whenever necessary. Because of the size of the sample, it is unlikely that the randomization will result in significant imbalance of the distributions of demographic or other variables across the treatment groups. However, some additional covariates will be considered for inclusion in the analyses, to improve the precision of estimation for the treatment effects (Hauk et al., 1998). In particular, we will consider covariates describing levels of alcohol and cocaine use prior to the study. In all analyses, the assumptions underlying the application of all the statistical methods that are used will be examined, principally through the use of standardized residuals, influence diagnostics, and graphical displays.

Primary Hypotheses:

Hypothesis 1: The outcome of interest is cocaine use, measured with three-times-weekly urine benzoylecgonine (BE) levels and self-reports of use from the Time Line Follow Back, combined to yield daily use/no-use indicators for each study day. We will be examining both point prevalence and continuous cocaine abstinence. A generalized estimating equations (GEE) model will be used to model the effects of group and time on the log-odds of use across the treatment period.

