The explanatory variables in these models will be a factor for group, and terms for time effects, and group by time interactions. In these models, we are interested in weekly rates of use, so time will be coded as weekly units, with up to seven daily indicators providing replications within a week. These models will provide valid estimates of the regression parameters (i.e. group and time effects) without requiring that the correlation between a subjects repeated urine drug screens is known. It is usually enough to specify a simple “working” correlation matrix, which need not agree with the true correlation matrix underlying the repeated measures. This provides a “robust” approach, but usually at the cost of larger sample sizes, and the lack of simple methods for comparing different models. Based on the work of Lipsitz,(Lipsitz et al., 1994), the sample size in this study will be more than adequate for the method to be valid. We will follow the recommendations of Pan and Connett (Pan and Connett, 2002) in selecting the working correlation matrix, and the recommendations of Pan (Pan, 2001a) in using an adjusted AIC statistic (his QIC statistic) to compare models. These analyses will be performed using PROC GENMOD in SAS.

Secondary Hypotheses:

Hypothesis 2 (effects of compliance with medication): The main analyses will be performed using an intent-to-treat (ITT) approach, so subjects will be analyzed according to their

assigned treatment, without reference to the level of treatment they actually receive. It is likely that some subjects will not comply with their assigned treatment, and that this non-compliance will be related to subject characteristics, and/or to unmeasured factors related to outcome. This non-compliance can diminish the extent to which the treatment groups are comparable with respect to measured and unmeasured variables. In this study, the placebo group will be unable to obtain varenicline, so non-compliance will probably result in underestimated treatment effects. We will gather information on compliance, and use it in further analyses to assess the sensitivity of the ITT analyses to the presence of non-compliance. The information will be obtained from weekly pill counts, on the basis of self-report and examination of blister packs.

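### The primary GEE as listed leaves out both urn factors and only considers pre-study cocaine use; fixing the covariates and one treatment contrast before unblinding would gain precision at little cost

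*Combined protocol and SAP*

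**What the plan says.** Section 7.2, under Hypothesis 1, lists the model terms: "The explanatory variables in these models will be a factor for group, and terms for time effects, and group by time interactions". The Study Summary gives the same list: "The explanatory variables in these models will be a binary factor for medication, and terms for time effects, and group by time interaction".

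Section 5.3 describes the allocation: "we will stratify subjects on 2 baseline variables: 1. Gender; 2. Cigarette smoking status". Neither variable appears as a model term anywhere in section 7.

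On other covariates, the opening of 7.2 says "some additional covariates will be considered for inclusion in the analyses, to improve the precision of estimation for the treatment effects", and then "we will consider covariates describing levels of alcohol and cocaine use prior to the study". It gives no final list, variable definition or inclusion rule, and does not say whether the adjusted or the unadjusted result is primary. Section 7.2 also plans to compare models by QIC, without limiting which parts of the model may be compared.

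The natural covariate is already collected. Section 6 says of the Timeline Follow Back: "The TLFB will be given by trained research staff at baseline to cover 3 months immediately preceding treatment entry". Section 4.3 lists among the screening procedures "assessment of baseline drug and alcohol use using the Timeline Follow Back", and section 6.1 adds: "All screening procedures are to be completed prior to randomization".

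**The concern.** The plan says that it wants precision and collects the variable most likely to provide it, yet the model it writes down does not use that variable. Two analysts could both follow 7.2 and report different primary results, one adjusted and one not.

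The treatment contrast is also open. With group-by-time in the model, the data yield no single treatment odds ratio until someone says which combination of coefficients answers Hypothesis 1: the average over the treatment weeks, the difference at the end, the interaction, or a joint test. Section 7.2 does not say.

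At stake are some power and the certainty that the primary result was chosen in advance. The validity of the unadjusted test is not in question.

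**Working it through.** **No figure to reproduce.** Section 7.1 gives alpha 0.05 and compound symmetry; section 3.1 gives 100 subjects per group. No use rates, effect size, correlation, power or dropout rate is stated, so 200 cannot be re-derived. Everything below rests on assumed values.

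**Step 1, precision from baseline use.** For a baseline covariate with correlation r with on-treatment use, the variance of the treatment effect falls by the factor 1−r², so effective N = 200/(1−r²). Take the unadjusted test to have 80% power (two-sided 0.05, assumed). The standardised effect is then 1.960 + 0.842 = 2.802, and adjusted power is Φ(2.802/√(1−r²) − 1.960).

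| r (assumed) | 1/(1−r²) | Effective N | Power, cut-off 1.960 | Power, cut-off 2.013 |
|---|---|---|---|---|
| 0.20 | 1.04 | 208 | 81.6% | 80.1% |
| 0.30 | 1.10 | 220 | 83.6% | 82.2% |
| 0.45 | 1.25 | 251 | 88.0% | 87.0% |
| 0.61 | 1.59 | 319 | 94.2% | 93.6% |

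The last column applies a small-sample correction to the robust SE with p = 8 parameters (intercept, group, linear and quadratic week, group-by-week, three covariates): √(200/192) × 1.972 = 2.013. The same correction on the five-parameter unadjusted model gives √(200/195) × 1.972 = 1.997 and takes its 80% to 78.9%. Like for like, the gain at r = 0.20 is therefore only about 1 point.

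**Step 2, check by simulation.** Assumed: 200 subjects, 12 weeks of 7 daily indicators, 25% female (50 of 200 in the section 10.1.a enrolment table), 75% smokers, between-subject SD 1.5 on the logit scale, urn-factor log-odds 0.4 each, independence working correlation and robust SE. The contrast is the average over weeks; the adjusted model contains baseline use and both urn factors.

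| r | Power unadjusted | Urn factors only | Adjusted | Variance ratio |
|---|---|---|---|---|
| 0.30 | 80.7% | 81.6% | 84.9% | 1.10 |
| 0.45 | 79.7% | 80.7% | 88.2% | 1.23 |
| 0.61 | 80.0% | 80.9% | 94.2% | 1.60 |

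The variance ratios agree with 1/(1−r²). With 35% dropout they are 1.09, 1.23 and 1.53. These powers carry no small-sample correction; at r = 0.30 the cut-off of 2.013 would take 84.9% to about 83.6%. Urn factors alone add 0.3 to 1.4 points, or about 3 points if their effects are doubled. Nearly all the gain comes from baseline cocaine use.

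**Step 3, validity.** In the same set-up under no effect, the unadjusted test rejected in 4.7–5.2% of trials, the adjusted test in 5.2–5.7% (5.4–6.0% in separate runs), and the adjusted test with the correction in 4.7–5.4%.

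**Step 4, the contrast.** In a second simulation (constant treatment log-odds of −0.75, 1,000 trials, no missing data), the same adjusted model gave 89% power for the average over the period, 84% for the joint test and 5% for the interaction alone. The last figure is only the alpha level, because a constant effect has no interaction.

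**Step 5, the estimand.** In the second simulation the treatment log odds ratio was −0.48 unadjusted and −0.54 adjusted, that is, odds ratios of 0.62 and 0.58. In the first simulation the marginal odds ratio was 0.65 and the conditional one 0.64, 0.63 and 0.62 at the three values of r. A covariate-adjusted logistic coefficient estimates a different quantity, so the label matters.

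**The case against.** The best objection is that 7.2 already intends adjustment for precision and names pre-study cocaine use. What is missing is a commitment, not the idea. Figures that compare never adjusting with adjusting therefore overstate the defect. This stands: the gains above are over the model as listed, and shrink to the extent that the statistician would have adjusted anyway.

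It is also fair that r is unknown. At 0.20 the gain is almost nothing, and adjustment slightly raises type I error unless the robust SE is corrected. Urn factors matter little for power; the reason to include them is that the allocation used them. Baseline Timeline Follow Back days are one reasonable choice among several: screening urine results are available too.

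Three stronger readings are tempting, and the documents do not support them:

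- A reader might infer that leaving out the urn factors makes the primary test biased or invalid. It does not; the robust GEE held its level without them.
- A reader might infer that open covariates mean the best p-value will be picked. Keeping the smallest of four covariate sets would give 7–11% type I error under the assumptions used, but the plan proposes no such thing.
- A reader might infer that fixing the covariates and the contrast settles the primary analysis. Other questions remain open: a mixed model beside the GEE in the Study Summary, point prevalence beside continuous abstinence in 7.2, and a urine-only hypothesis in 3.2 against a combined urine and self-report outcome in 7.2.

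**Conclusion.** The point holds as a worthwhile improvement to a valid analysis. The listed model omits both urn factors, baseline cocaine use is optional although it is in hand before randomisation, and no contrast is named.

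The possible loss is precision: an effective sample size larger by about 4% to 59% for r from 0.20 to 0.61, slightly less benefit after a small-sample correction, and less again if adjustment would have happened anyway. From 80% power, that is roughly 82% to 94% before correction. These figures rest on an assumed r, an assumed 80% starting power and the period-average contrast; none comes from the documents.

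Naming the contrast does not depend on r. It is needed whichever covariates are chosen.

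**What to change.** Amend 7.2, and align the Study Summary, before unblinding. Section 10.1 plans efficacy analysis only at trial end, with no interim analyses.

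1. Primary GEE: group, time and group-by-time, plus gender, smoking status as coded for the urn, and cocaine-use days from the baseline Timeline Follow Back. Make the unadjusted model a sensitivity analysis, and use pre-study alcohol use only in a further one.
2. Primary contrast: the group effect averaged over the 12 treatment weeks (study weeks 2–13). Exclude screening week 1 from the outcome period, since it could overlap the baseline window, and reconcile this with the 13-week trend in the Study Summary. Fix the form of time and of group-by-time in advance.
3. Use QIC only to choose the working correlation, not covariates, the form of time or treatment terms.
4. Label the odds ratio conditional or marginal. A standardised odds ratio and a small-sample robust SE are optional refinements.

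The cost is a little more SAP text and programming. No added subjects, visits or data are needed. The open questions on model type, abstinence measure and outcome source need their own amendment.

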3.1 General Design

This is a Phase II double-blind randomized controlled clinical trial. The hypotheses in the proposed study will be tested with a 2-group design to assess the efficacy of varenicline as compared to placebo. We will follow NIAAA's COMBINE Medical Management (MM) manual in weekly dispensing medications, safety checks and medication adherence. The psychosocial treatment will be Cognitive Behavioral Coping Skills Therapy (CBT). Subjects will be 200 men and women with current DSM-IV diagnoses of cocaine dependence that will be randomized to receive either varenicline or placebo (100 subjects per group). All subjects will

receive weekly sessions of CBT. The study length for each subject is comprised of 1-4 weeks of screening (referred to as “week 1”) and a 12-week double-blind, placebo-controlled trial with CBT (medication phase). *At the end of the study subjects will be referred to continuing care programs in the community.*

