3.3 Secondary Study Endpoints

Secondary Hypotheses:

- We further hypothesize that within the varenicline group, medication compliant participants ($\geq 80\%$ of pills taken) will have higher rates of cocaine abstinence than those who are non-compliant ($< 80\%$ of pills taken).
- We expect that the varenicline group will report less craving for cocaine than will the placebo group, as measured by lower scores on the Cocaine Craving Questionnaire (Tiffany et al., 1993) and the Minnesota Cocaine Craving Scale (Halikas et al., 1991) during the medication treatment phase.
- We expect that the varenicline group will show greater decreases in cigarette smoking than will the placebo group, as evidenced by CO and cotinine levels.

• Primary Safety Endpoints

A nurse or physician will assess for adverse events weekly. Adverse events will be monitored by research staff at all other visits, and the psychiatrist or nurse will be available at other visits to assess the subject if needed. At the conclusion of medications, an end of study physical will be completed and the baseline laboratory tests, including EKG, will be repeated. If the subject is discontinued in treatment due to a serious adverse event, the subject will be followed clinically by medical staff until the adverse experience resolves itself and becomes stable.

4 Subject Selection and Withdrawal

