11. **Medical history & Physical exam (PE)** A complete medical history and physical exam will be conducted by the nurse or physician at Visit 1. The physical exam will be repeated at visit 40.
12. **Minnesota Cocaine Craving Scale** (MCCS) (Halikas et al., 1991). The MCCS is a valid and reliable measure of cocaine craving. Craving is assessed over three dimensions, intensity, duration, and frequency and subjects are asked to evaluate their craving for the prior week. The MCCS will be administered at baseline, weekly throughout the medication phase of the trial, once at the end of randomized medication phase (Visits 1, 4, 7, 10, 13, 16, 19, 22, 25, 28, 31, 34, 37, 40).
13. **Multiple Choice Procedure (MCP)** (Griffiths, Troisi II, Silverman & Mumford, 1993) This adaptation of the MCP asks participants to choose between a hypothetical static amount of cocaine and hypothetical variable amounts of money. Repeated administrations of the MCP allow for assessment of changes in the relative reinforcing effects of cocaine over time, evidenced by shifts in how much participants are willing to “pay” for a static amount of cocaine (visits 1, 4, 7, 10, 13, 16, 19, 22, 25, 28, 31, 34, 37, 40).
14. **Pill Count** The number of capsules of study medication dispensed and the number returned each week will be recorded in the CRF (visit 4, 7, 10, 13, 16, 19, 22, 25, 28, 31, 34, 37, 40).
15. **Structured Clinical Interview for DSM-IV (SCID) (First et al., 1996), Mini-International Neuropsychiatric Interview (MINI) (Sheehan et al., 2002)** The substance abuse module (Module E) of the SCID-IV will be used to diagnose substance abuse problems. The major depressive episode modules (Modules A and B) of the MINI Plus will be used to diagnosis current and past episodes of major depression and current episodes of major depression with melancholic features. Other lifetime DSM-IV Axis I and II diagnoses will be obtained from the MINI. The SCID/MINI/MINI Plus will be done once during baseline to confirm diagnoses

of cocaine and alcohol dependence and determine if Axis I, Axis II or other substance disorder diagnoses are present. Time of administration will be 45 minutes. The SCID/MINI/MINI Plus will be administered by a clinically-trained Diagnostic Interviewer.

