7.1 Sample Size Determination

Power Analysis

Based on the results of our pilot trial (Plebani et al., 2011), we use the method described by Diggle et al. (1994) to estimate power, assuming a compound symmetry covariance structure. We assume a Type-I error level (Alpha level) of 0.05.

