Initially, we will use these sources to determine whether each subject has complied with their assigned medication for at least 80% of the trial. We will then include a binary variable indicating “80%” compliance in the analyses described above for Hypothesis 1, both as a main effect and as an interaction effect with varenicline group.

We will also use the sources described above to define variables representing compliance/non-compliance over each the 12 weeks of the treatment period. For the primary outcomes, we will perform extensions of instrumental variable regression analyses presented by Nagelkerke et al. (Nagelkerke et al., 2000). Here the instrumental variable is randomization and, under certain assumptions, will control for unmeasured bias when estimating the effect of varenicline relative to placebo in those who comply with their assigned treatment. These analyses will permit a more complete examination of the time-varying effects of compliance across the treatment period.

Hypothesis 3: The CCQ and MCC scales will provide weekly measures of cocaine craving. The scales provide a seven and a six-category Likert response, respectively, and it is likely that we will collapse some adjacent categories prior to the analyses, and regard the responses as ordinal. The analyses for these hypotheses will be perfectly analogous to those for Hypothesis 1, except that mixed-effects models for ordinal responses will be used (Hedeker and Mermelstein, 2000). These analyses will be performed using PROC NLMIXED in SAS.

Hypothesis 4: The CO and cotinine measures will be used to analyze dynamic changes in cigarette smoking, both in isolation and as they relate to cocaine use.

Other Analytic Issues:

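### The craving analyses do not prespecify the subject's own pre-randomization score as a covariate, and the smoking analysis names no reference for a decrease: a free gain in precision on secondary outcomes

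*Combined protocol and SAP*

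**What the plan says.** Section 3.3 expects less craving on the CCQ and MCCS in the varenicline group during medication treatment. For smoking it states: "We expect that the varenicline group will show greater decreases in cigarette smoking than will the placebo group", judged by CO and cotinine.

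Section 7.2, Hypothesis 3, gives the craving analysis by reference: "The analyses for these hypotheses will be perfectly analogous to those for Hypothesis 1, except that mixed-effects models for ordinal responses will be used". The Hypothesis 1 template reads: "The explanatory variables in these models will be a factor for group, and terms for time effects, and group by time interactions". The general paragraph at the start of 7.2 allows additional covariates to be considered for the sake of precision, and then says: "In particular, we will consider covariates describing levels of alcohol and cocaine use prior to the study". It gives no rule for deciding which covariates enter.

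Hypothesis 4 is a single sentence. CO and cotinine are to be used to study changes in smoking, with no model, response variable, covariate or reference value.

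The baseline values exist. Section 6 (instrument 12) says: "The MCCS will be administered at baseline, weekly throughout the medication phase of the trial, once at the end of randomized medication phase". The CCQ has the same visit list, starting at Visit 1. CO and cotinine are taken at every visit from 1 to 40, which gives up to three readings before randomization. Section 6.1 requires screening procedures to be finished before randomization, though not always at the listed visit.

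**The concern.** A subject's own earlier score is usually among the best predictors of later scores on the same scale. If it is not in the model, stable differences between subjects in craving remain in the error of the average treatment contrast. The test on the same 200 subjects is then weaker than the collected data allow. The general paragraph of 7.2 wants covariates for precision, but does not name the one most likely to serve that aim for these outcomes.

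A covariate that is only to be considered, with no inclusion rule, also leaves the choice open until outcomes have been seen. For smoking, the hypothesis concerns a decrease, but the written analysis does not say from what value.

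**Working it through.** **The plan's own figure.** Section 3.1 gives 200 subjects, 100 per group. Section 7.1 says only "We assume a Type-I error level (Alpha level) of 0.05" and that a published longitudinal method was used "to estimate power, assuming a compound symmetry covariance structure". It states no effect size, SD, correlation or power, so 200 can be neither reproduced nor refuted. The check below concerns relative precision only.

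**Inputs.**
- From the documents: 100 per arm; alpha 0.05 (two-sided assumed); 12 weekly craving scores at Visits 4 to 37; one pre-randomization score; compound symmetry.
- Assumed, because the documents give none: correlation rho between weekly scores, and correlation rb between the baseline and each weekly score. Scores have unit SD, and no dropout is applied.

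**Formulas for the average over 12 weeks.**
- Unadjusted variance per subject: V = (1 + 11·rho)/12.
- Share removed by adjusting for one baseline: r² = rb²/V.
- Equivalent sample size: 200/(1 − r²).

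| rho | rb | V | r² | Adjusted/unadjusted variance | Equivalent N |
|---|---|---|---|---|---|
| 0.2 | 0.2 | 0.267 | 0.04/0.267 = 0.15 | 0.85 | 235 |
| 0.3 | 0.3 | 0.358 | 0.09/0.358 = 0.25 | 0.75 | 267 |
| 0.5 | 0.3 | 0.542 | 0.09/0.542 = 0.17 | 0.83 | 240 |
| 0.5 | 0.5 | 0.542 | 0.25/0.542 = 0.46 | 0.54 | 371 |
| 0.7 | 0.7 | 0.725 | 0.49/0.725 = 0.68 | 0.32 | 617 |

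With a common correlation of 0.2, 0.3 or 0.5, the standard error falls by 8%, 13% or 27%. An effect with 80% power unadjusted would have 86%, 90% or 97% power adjusted. The 0.7 row shows the direction beyond the quoted range; the conclusion does not rely on it.

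**Simulation check.** With a random intercept, 12 weeks and 4,000 runs per correlation, the variance ratios for the average contrast at 0.3, 0.5 and 0.7 were 0.74, 0.55 and 0.32. The formula gives 0.75, 0.54 and 0.32. For the week-by-group slope the ratio was about 1.01 each time, so there is no gain.

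**Change scores are not a safe substitute.** The variance of the 12-week mean minus one baseline is V + 1 − 2·rho. At rho 0.3 this is 0.358 + 1 − 0.6 = 0.758, or 2.1 times the unadjusted variance. At 0.5 the two are equal, and at 0.7 the ratio is 0.45.

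**Smoking, for scale only.** Treat CO or cotinine as continuous, with 36 on-treatment visits and the mean of three screening readings. Then V = (1 + 35·rho)/36, B = (1 + 2·rho)/3, and adjusted variance is V − rho²/B. The ratio to V is 0.61, 0.47 and 0.27 at rho 0.2, 0.3 and 0.5. No such model is written in the plan, and the dipstick reading may not be continuous.

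**The case against.** - **Baseline craving is not excluded.** The covariate sentence gives examples, not a closed list. Prior cocaine use is the own-baseline covariate for Hypothesis 1, so an analogous craving model could be read as carrying baseline craving. This stands. A reader might infer that the models shut baseline out, but the documents show only that it is unnamed and optional.
- **Week 1 may already be a response.** The Study Summary describes time trends over 13 weeks, and screening is called week 1. On that numbering the baseline could sit in the outcome series. Section 7.2, however, models use across the treatment period. The text is ambiguous and should be settled.
- **The gain depends on the contrast.** The plan does not say which term is the test, and the slope gains nothing. This stands. The wording of 3.3, less craving during treatment, points to the average level, where the gain applies.
- **Part of the gain may already be available.** If prior cocaine use is included and correlates with baseline craving, some of the precision is recovered. This stands, and its size cannot be judged from the documents.
- **There is no smoking model from which to omit anything.** This is correct. A reader might infer that a smoking model leaves out baseline, or that the trial lacks a reference value. Neither is supported: Hypothesis 4 states no model, and CO and cotinine are measured at Visits 1 to 3. The urn also stratifies on smoking status (5.3), which limits imbalance between smokers and non-smokers, though not in CO or cotinine level.

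**Conclusion.** The point holds as one of precision and prespecification. The plan does not commit to the subject's own pre-randomization CCQ or MCCS score, although it is collected. For the average-level contrast, adjustment would remove about 15% to 46% of the variance at assumed correlations of 0.2 to 0.5. These figures are linear approximations to an ordinal mixed model and ignore dropout.

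A reader might go further and infer that the craving comparison is biased. The documents do not support that. Under randomization, chance baseline differences are part of the sampling error that the standard error already reflects; the cost is lost precision.

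For smoking, the gap is that the written analysis defines neither a model nor the reference for a decrease. The primary hypothesis is untouched. This is a free improvement to secondary outcomes, of low to moderate severity.

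**What to change.** In 7.2, Hypothesis 3: include the pre-randomization score of the same scale (nominally Visit 1) as a fixed covariate in each CCQ and MCCS model, whatever its p-value. State that screening week 1 is a covariate and not a response, and align the Study Summary's 13-week wording with this.

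In 7.2, Hypothesis 4: write down a model for CO and one for cotinine, each adjusted for the screening (Visits 1 to 3) value. For cotinine, use the dipstick's own scale and say how its screening readings are combined, since a mean presumes a numeric score. Smoking status, as an urn factor, should be a term. The decrease then has a stated reference.

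The craving change costs a few lines. The smoking change costs somewhat more, because the model itself has to be specified. Neither needs new data or visits.
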